**Ultrasound Measurements and Criteria:**

The criteria for complete occlusion (occlusive) were absence of flow with distal augmentation and incompressibility of the vein. Minimal clot will be defined by wall thickening, webbing, etc. Partial recanalization will be defined by >50% or <50% normal or diminished flow with distal augmentation and partial incompressibility of the vein. Complete recanalization (resolved or no clot) will be defined by spontaneous phasic flow and a completely compressible vein and no residual clot (see Table 2).

Table 2.0

Site	No Residual Clot	Minimal Clot (wall thickening, webbing, etc)	Recanalized >50%	Recanalized <50%	Near Occlusive	No Change	Worse Or Extension
External Iliac (EIV); if evaluated							

Common femoral (CFV)							
Femoral- Upper (FV)							
Femoral - Middle							
Femoral - Lower							
Deep femoral (DFV)							
Popliteal (PV)							
Posterior tibial (PT-calf)							
Gastrocnemius (G-calf)							
Peroneal (P-calf)							
Soleal (S-calf)							
Total							

**Study Procedure**

All subjects included in this study will have a diagnosis of deep vein thrombosis that will undergo standard anticoagulation with or without wearing a vascular boot. Medical charts will be abstracted for clinical, laboratory, medications, imaging and pathologic findings. Subjects will undergo their initial (baseline) clinically indicated DVT ultrasound for diagnosis of lower extremity DVT. The second clinically indicated limited venous ultrasound will be completed on post-DVT day 90 (14±days) to evaluate resolution. Research ultrasound intervals will then occur on days 0 (+1 days), 3 (-2/+5 days), 10 (±5 days), and 90 (14±days). Shear wave elastography will be conducted at all post-treatment ultrasound intervals. We will compare the shear wave elastography to the opposite lower extremity veins on the same individual for a control if DVT is not present in that extremity at that time or previously.

Commercially available ultrasound systems (Logiq E9, GE Medical Systems, Milwaukee, WI, USA) equipped with phased-array and linear transducers will be utilized. Longitudinal and short axis images of each clot will be acquired and digitally stored for offline analysis. The short axis images will be acquired. 2-D images, 2D shear wave and elastography images will be acquired and digitally stored for off-line analysis. All measurements will be made in a blinded fashion by a single observer.

**Shear Wave Elastography:** The subject will be asked to lay on a hospital bed for ultrasound imaging. The veins of the lower extremity will be visualized using ultrasound imaging, and the depth of the venous wall will be noted. The focal depth on the device will be set to measure shear wave propagation in the walls of the vein and in the thrombus. Measurements will be made at multiple locations along the veins length.

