### **Secondary Objectives**

1. Determine if early vascular boot warming plus standard anticoagulation (after 24 hours of anticoagulation therapy from time of diagnosis) is a safe intervention after diagnosis of acute DVT±PE.
2. Determine if vascular boot warming plus standard anticoagulation improves or accelerates the resolution of the clot among those with DVT±PE.
3. Determine if vascular boot warming plus standard anticoagulation improve the venous functional study measures of calf pump ejection fraction, VFR, PDR T90, and overall venous performance score.
4. Determine whether a vascular boot warming plus standard anticoagulation can improve the quality of life in patients with venous insufficiency or previous history of deep vein thrombosis of the lower extremity ± PE.
5. Identify difference in activity level between those who underwent a vascular boot warming program/activity plus standard anticoagulation versus standard anticoagulation only.
6. Analyze whether shear wave elastography will provide a more accurate and reliable method to assess the age of thrombosis and better quantification of thrombosis resolution.
7. Collect natural history data of post-thrombotic syndrome.

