**Inclusion Criteria**

1. Age ≥18
2. Able to tolerate wearing a vascular boot, if randomized to this group.
3. Diagnosis of acute DVT±PE (within 24 - 48 hours) and received approximately 24 hours of anticoagulation prior to starting the study.

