## Study Design

### Methods

Patients with diagnosis of acute lower extremity DVT (proximal and distal) and/or pulmonary embolism will be identified and approached for participation, when they are seen in the Thrombophilia Clinic or Mayo Hospital for management of the acute VTE. If they match the preset inclusion and exclusion criteria, they would then be consented during this visit and scheduled for baseline studies at a later date.

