#### Baseline studies will include:

- (1) Venous plethysmography: (ejection fraction, VFR, PDR T90, EDV T90, MV, F1.0).
- (2) Lower Extremity Ultrasound: DVT (thrombus) evaluation with 2-D ultrasonography (standard) and shear wave elastography (done within 1 day of baseline clinical ultrasonography).
- (3) Other relevant clinical information (such as height, weight, BMI, bilateral calf circumference, edema, leg pain, ulcerations, previous LE surgery, use of compression stockings, and any current set exercise program). Demographical data, common vascular risk factors (including tobacco use, coronary and peripheral arterial occlusive disease, diabetes, hypercholesterolemia, and hypertension) and the treatment information, will be obtained from chart review via ACE database and Synthesis. All data will be entered and stored in RedCap research tool.
- (4) Anatomic distribution of thrombi at initial examination will be documented as single segment and/or multi-segment(s) involved. The segments will be label as: external iliac vein (EIV), only if clot extends above the common femoral vein; common femoral vein (CFV); femoral vein (FV) (upper, middle, lower); deep femoral vein (DFV); popliteal vein (PV); posterior tibial vein (PTV); gastrocnemius (G-calf); peroneal vein-calf (PV-calf); soleal vein-calf (SV-calf) (see Table 1).

Table 1.0

Site	Anatomic Distribution of Thrombi			
	Initial	3 days	10 days	3 months
Single Segments				
External Iliac (EIV); if evaluated				
Common femoral (CFV)				
Femoral- Upper (FV)				
Femoral - Middle				

Femoral - Lower				
Deep Femoral (DFV)				
Popliteal (PV)				
Posterior Tibial (PT-calf)				
Gastrocnemius (G-calf)				
Peroneal (P-calf)				
Soleal (S-calf)				
Total				
Multisegment				
EIV- CFV				
EIV- CFV-FV				
EIV- CFV-FV-PV				
EIV- CFV-FV-PV-calf				
CFV-FV				
CFV-FV-PV				
CFV-FV-PV-calf				
FV-PV				
FV-PV-calf				
Total				

Patient will then be randomized to vascular boot plus standard anticoagulation program or standard anticoagulation using the randomizer built into RedCap.

**Standard of Care (SOC) Group (no vascular boot utilized)**: Patients will receive standard anticoagulation (determined at discretion of the treating provider), baseline studies, and follow up at the end of treatment (3months).

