**Vascular Boot (VB) Group (includes vascular boot in addition to SOC)**: Patients will receive standard anticoagulation (determined at discretion of the treating provider), baseline studies and standardized vascular boot warming (see below). All patients randomized to this group will wear the vascular boot for a minimum of 30 minutes per day for the first 10 days of participation. Patients in this group may initially be enrolled at either the thrombophilia clinic or the hospital.

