**Follow up data (SOC and VB Groups) include:**

- (1) Ultrasound of the leg with DVT and leg circumference measurement at 3 days, 10 days, and 3 months. Ultrasound data will include data on thrombus resolution, such as size and recanalization present.
- (2) Venous plethysmography at 3 months.
- (3) Study Questionnaires:
  - a. Godin questionnaire (validated questionnaires to measure physical activity)
  - b. VEINES-QOL (generic physical quality of life questionnaire)
  - c. Villalta Score (to assess Post-Thrombotic Syndrome)

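### The day-10 scan window opens on day 5, so a compliant scan can fall about halfway through the 10-day boot course

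*Combined protocol and SAP*

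**What the plan says.** The Study Procedure section of the combined protocol and SAP gives the research scan days with their tolerances: "Research ultrasound intervals will then occur on days 0 (+1 days), 3 (-2/+5 days), 10 (±5 days), and 90 (14±days". The section on follow-up data gives the nominal times for both arms: "Ultrasound of the leg with DVT and leg circumference measurement at 3 days, 10 days, and 3 months".

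The paragraph on the Vascular Boot group says that its patients "will wear the vascular boot for a minimum of 30 minutes per day for the first 10 days of participation". Three places bear on when participation starts:

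- Inclusion criterion 3 requires "Diagnosis of acute DVT±PE (within 24 - 48 hours) and received approximately 24 hours of anticoagulation prior to starting the study".
- The first secondary objective places boot use "after 24 hours of anticoagulation therapy from time of diagnosis".
- Under Methods, consented patients are "scheduled for baseline studies at a later date", and randomisation is described after those baseline studies.

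Day 0 is not defined. Two statements point towards diagnosis. The clinical scan is dated from the event: "The second clinically indicated limited venous ultrasound will be completed on post-DVT day 90 (14±days) to evaluate resolution". The baseline elastography is to be "done within 1 day of baseline clinical ultrasonography", which matches the +1 day tolerance on day 0. The sentence that sets the research scan days names no anchor of its own.

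The primary endpoint in the Endpoints section is early resolution on ultrasound. No scan day is attached to it.

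**The concern.** Two clocks run side by side. The boot course is counted from the start of participation. The scans are counted from a day 0 that may be diagnosis, randomisation or the first session. With a symmetric 5-day tolerance, the day-10 scan can be taken while the course is still under way and yet be fully within protocol.

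This matters because the day-10 scan is the only early one placed near the end of the course. The day-3 scan is an interim look, and the next scan is at 3 months. If some day-10 scans are taken mid-course, part of the contrast between the arms is lost at that visit. The Background also cites work in which regression over the first one to three weeks was close to exponential, so a day 5 to day 15 spread mixes different stages of natural resolution. With 15 patients per arm, avoidable variability is worth removing.

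**Working it through.** The plan states no figure to reproduce here. The check is a count of days.

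**Inputs**

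- Day-3 window: 3 - 2 = day 1 to 3 + 5 = day 8 (Study Procedure).
- Day-10 window: 10 - 5 = day 5 to 10 + 5 = day 15, which is 11 permitted days (Study Procedure).
- Course: 10 daily sessions (Vascular Boot group paragraph).
- Day of first session, *s*: not fixed by the documents. I take *s* = 0 if day 0 is the first boot day, and *s* = 1 or 2 if day 0 is diagnosis and the start follows 24 to 48 hours later.

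**Formula.** For a scan on day *d*, the sessions done lie between min(10, max(0, *d* - *s*)), if the scan comes before that day's session, and min(10, max(0, *d* - *s* + 1)), if it comes after.

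| First session | Last session | Sessions by a day-3 scan on day 1 | Sessions by a day-10 scan on day 5 | Sessions by a day-10 scan on day 10 | Window days (of 11) before course is complete |
|---|---|---|---|---|---|
| day 0 | day 9 | 1-2 | 5-6 | 10 | 4-5 |
| day 1 | day 10 | 0-1 | 4-5 | 9-10 | 5-6 |
| day 2 | day 11 | 0 | 3-4 | 8-9 | 6-7 |

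At the early edge, the day-10 scan therefore follows at most 6, 5 or 4 sessions. A day-3 scan on day 1 can precede all boot use if the first session is on day 2, or on day 1 with the scan done first. It cannot if the first session is on day 0.

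**Average over the window.** Assume scans are spread evenly over days 5 to 15, with the scan day's session already done:

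- *s* = 0: (6 + 7 + 8 + 9 + 7 × 10) / 11 = 100/11 = 9.1
- *s* = 1: (5 + 6 + 7 + 8 + 9 + 6 × 10) / 11 = 95/11 = 8.6
- *s* = 2: (4 + 5 + 6 + 7 + 8 + 9 + 5 × 10) / 11 = 89/11 = 8.1

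If the scan always comes before that day's session, the averages are 95/11 = 8.6, 89/11 = 8.1 and 82/11 = 7.5.

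**Dilution.** Assume also that the effect is proportional to sessions done, which the documents do not support or refute. The average loss is then 1 - 0.91 = 9% to 1 - 0.81 = 19%, or 14% to 25% on the lower counts. A loss of 40% to 60% (1 - 0.6 to 1 - 0.4) would need essentially every day-10 scan to be taken on day 5.

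**With the proposed change.** If day 0 is the first boot day, the sessions fall on days 0 to 9. A scan on day 10 follows min(10, 10 - 0) = 10 sessions, even if it is early in the day. The mean of days 10 to 15 is 75/6 = 12.5, against 10 for days 5 to 15.

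**The case against.** The strongest reply is that a window permits early scans and does not call for them. The target is day 10, where 8 to 10 sessions are done, and even an even spread gives 8.1 to 9.1. That stands. A reader might infer that the early scans do not measure the course under test; the documents do not support that. Nor is the day-3 scan at fault for missing most of the course, since at its target day it can only be an interim look.

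The day-3 point is also conditional. The count from the DVT is attached to the clinical scan and not to the research scans. The Study Procedure section also describes the elastography scans as coming after treatment. If day 0 is the first boot day, a day-3 scan cannot precede boot use. What stands regardless is that day 0 is undefined.

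A reader might also infer that a null result could not be told apart from an undelivered course. That goes too far. Total boot-wearing time over the 10 days is recorded, individual dates are kept, and the 3-month scan follows the completed course in both arms. Scan timing could be examined afterwards, although the Data Analysis Plan names no such analysis. Because the windows are the same in both arms, the spread is not a source of bias by itself, although timing could differ by chance with 15 per arm.

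Finally, this is a 30-patient pilot with no sample size calculation, and the endpoint names no scan day, so day 10 is not established as the decisive scan. That limits the importance of the point. It does not explain why the window should open mid-course.

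**Conclusion.** The point holds as a cheap improvement. A scan labelled day 10 can comply with the protocol after only about half of the sessions: at most 4 to 6 of 10, for a first session on day 2 to day 0. Depending on how day 0 is read, a compliant day-3 scan can precede any session.

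The likely size is modest. On-target scans follow 8 to 10 sessions. The 9% to 19% average dilution rests on two assumptions: scans spread evenly over the window, and an effect proportional to sessions. The documents say nothing on either, and actual scheduling may cluster nearer day 10. The 40% to 60% figure describes the window's edge and should not be read as an expected loss. The expected harm is some loss of contrast and more variability at the only early scan near the end of the course.

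**What to change.** In the Study Procedure section:

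1. Count the follow-up research scans in both arms from one common day 0, defined as the first day of participation. State that this is the day of randomisation and that the boot days are counted from it too. Anchoring to randomisation alone would not be enough, because the documents do not equate it with the start of participation. If the first session fell on day 1, a day-10 scan could again follow only 9 sessions.
2. Make the day-10 window one-sided so that it cannot open before the 10-day period ends, for example -0/+5.
3. Allow no follow-up scan before the first day of participation is complete.

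The baseline scan keeps its present tie to the clinical ultrasound and is best labelled baseline, so that it does not share the day-0 label. The boot schedule is unchanged. As a by-product, the day-3 window (days 1 to 8) and the day-10 window (days 10 to 15) no longer overlap on days 5 to 8.

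The cost is a small edit to the scan-timing text and the visit calendar, less flexibility in booking, a somewhat later average scan day (12.5 against 10 under an even spread), and a few more out-of-window scans.

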O'Shaunessy et al reported that 60% of their patients had completely resolved their thrombus by the end of 1 year. This study examined 63 above-knee DVT anatomic segments with duplex scanning at 1 week, 1 month, 6 months, and 1 year after the acute event. The segments under investigation were the external iliac vein (EIV), common femoral vein (CFV), superficial femoral vein (SFV), and popliteal vein (PV). Initially, a greater number of segments were occluded (71%) than partially thrombosed (29%). The occluded segments were predominantly in the SFV and PV. At 1 year the thrombi had fully resolved in 60% of the venous segments, 27% remained partially recanalized, and 13% were occluded. At 1-year follow-up the thrombus had fully resolved in 103 segments: 94% of the EIVs, 78% of the CFVs, 42% of the SFVs, and 54% of the PVs. Of these, 61% of the segments were found to be competent without reflux flow, and 39% were incompetent with reflux flow of greater than 1 second. The time involved for individual segments to fully recanalize varied from 1 week to 1 year. Segments that resolved within the first 6 months had a higher frequency of valvular competency than incompetency ( $P > .006$ ). The segments that resolved after 6 months had a higher incidence of incompetency to competency (31:13), but this was not statistically significant. The SFV and PV had a higher incidence of valvular incompetence than the EIV and CFV. All venous segments that were partially recanalized at 1 year were found to have significant reflux. The SFV had the highest incidence of total occlusion at the end of 1 year (36%). Many of the occluded SFVs had established collateral pathways that displayed no evidence of reflux. Ramshorst et al. observed thrombosis resolution to occur in the first 1 to 3 weeks after acute DVT and appeared to occur at an almost exponential rate. They noted that recanalization occurred mainly in the first 6 weeks after diagnosis, but clot resolution eventually occurred in 75% of the thrombosed segments within 6 months. Caprini et al. reported that complete resolution had occurred in more than 40% of thrombosed venous segments within 3 months after the diagnosis of DVT, and lysis had occurred in more than 70% of segments within 6 months of treatment.

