### **Study Rationale Innovation and significance:**

Warming of the lower extremity enhances blood flow in the treatment of superficial vein thrombosis and has been well established. However, the effect of vascular boot warming plus standard anticoagulation on deep venous disease progression is unknown and may prove to reduce DVT with standard anticoagulation more effectively and quicker with reduced risk for PTS. To date, there is no randomized control study evaluating the effect of vascular boot warming plus standard anticoagulation in venous insufficiency. We hypothesize that the combination of vascular boot warming and standard anticoagulation will result in improvement in calf muscle pump function, thus improvement in venous physiology and quicker resolution of DVT and associated clinical symptomatology of post thrombotic syndrome. Ultrasonography with shear wave elastography imaging is a novel ultrasound technology that potentially can quantify and assess thrombosis age, evolution of thrombosis, and risk of detachment. These evaluations can be readily performed in the patient's examination room on a single ultrasound system. The overall anticipated results of our research proposal are to demonstrate that: 1) DVT may resolve more effectively with a vascular boot through warming evaluated by standard 2-D ultrasonography with compression (standard therapy); 2) shear wave elastography is a feasible diagnostic tool in those with lower extremity thrombosis; 3) shear wave elastography can provide a more accurate and reliable method to assess the age of thrombosis and better quantification of thrombosis resolution while assessing the natural history, progression, and risk of detachment; 4) this technology can readily be incorporated into the daily workflow to improve diagnostic and prognostic value for detection of DVT and resolution [It has been estimated that the average image acquisition time to be added to a standard ultrasound study is minimal (7-10 minutes for shear wave elastography imaging) 5) these techniques can improve prediction of complications among those with DVT and; 6) these techniques can help decrease the number of age indeterminate thrombus that may result in unnecessary treatment with anticoagulation and its associated risks.

**Subject Information** – charts, records, images, or specimens are considered ‘subjects’

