*Target accrual is the proposed number of subjects to be included in your study at your site. “Subjects” may include Mayo Clinic charts, records, or specimens, **and/or** charts, records, or specimens received at Mayo Clinic from external sources for collaborating analysis by the investigator under this IRB application:*

**Target accrual:** 30 patients (15 patients with vascular boot vs 15 patients without vascular boot)

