**Exclusion Criteria**

1. Unable to tolerate wearing a vascular boot
2. Unable to comply with keeping log of activity/ of wearing a vascular boot.
3. Weight > 300 pounds. (*weight limit for the venous plethysmography chair*)
4. Previous history of DVT or PE.
5. On anticoagulation for another purpose (example stroke prevention with atrial fibrillation).
6. Patients who do not accept to participate in research studies.
7. Pregnant women will not be allowed to participate
8. Patients less than 18 yrs

Yes  No Will a Certificate of Confidentiality (COC) be obtained from NIH?

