**Statistical Considerations**

**Data Analysis Plan:**

This is a pilot study including 30 volunteers. Sample size cannot be calculated statistically due to lack of prior studies in the literature for those with DVT and use of warming boot. We will recruit up to 30 subjects who have valid measurements as described in the Data Analysis plan.

The ultrasound measurements (elastography) will be assessed for validity using data analysis techniques and to examine the visualization of the venous wall to see if we can quantify the thrombosis.

All statistical tests will be 2-tailed at a significance level of  $P < 0.05$ . Demographic and physical characteristics laboratory values and comorbid conditions will be presented as mean  $\pm$  standard deviation for continuous variables and as frequencies and percentages for categorical variables. Counts and percentages will be presented for categorical variables, while means  $\pm$  standard deviations and 95% confidence intervals will describe continuous variables for which normality assumptions are met. If the distribution of a continuous parameter is skewed, transformations will be considered, or medians and interquartile ranges (IQR) will be presented. Continuous variables will be compared between 2 groups using unpaired t-tests. For comparison of continuous variables in  $\geq 3$  groups, one-way analysis of variance (ANOVA) followed by a Scheffé test may be performed. Frequencies will be compared using Chi square analysis. The correlation between 2 continuous variables will be determined using a linear regression analysis. Cox proportional hazards regression will be used to estimate the

association between thrombosis and short-term and long-term outcomes. Logistic regression will be used to estimate the association between thrombosis and binary outcomes. Adjustment for potential confounders will be accomplished through, either, covariance regression modeling, propensity score stratification, or propensity matching, according to the discretion of the statistical analyst. Statistical analyses will be performed using SAS and/or R software.

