### **Secondary:**

- i. Improvements in calf muscle function as measured by venous plethysmography (ejection fraction, VFR, PDR T90, EDV T90).
- ii. Improved quality of function : Godin questionnaire (validated questionnaires to measure physical activity), VEINES-QOL (generic physical quality of life questionnaire) and Villalta Score (to assess Post-Thrombotic Syndrome)
- iii. Analyze whether shear wave elastography will provide a more accurate and reliable method to assess the age of thrombosis and better quantification of thrombosis resolution.

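### Day-90 thrombus stiffness exists only in clots not completely resolved, and the listed unpaired methods would let that selection pass for clot ageing

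*Combined protocol and SAP*

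**What the plan says.** Elastography serves secondary objective 6 and secondary endpoint iii: "Analyze whether shear wave elastography will provide a more accurate and reliable method to assess the age of thrombosis", together with better quantification of resolution.

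- **Schedule.** The Study Procedure section says "Shear wave elastography will be conducted at all post-treatment ultrasound intervals". Research scans fall on days 0, 3, 10 and 90, each with a window. The Baseline studies list also places elastography within a day of the baseline clinical ultrasound.
- **Target.** The Shear Wave Elastography paragraph aims the measurement at both the vein wall and the thrombus, at several locations. The opposite leg serves as control if it is free of DVT.
- **Resolution.** Under Ultrasound Measurements and Criteria, complete recanalization means a fully compressible vein with no clot left. Table 2 grades each site and includes a No Residual Clot column.
- **Expected clearing.** The Background cites a cohort in which "complete resolution had occurred in more than 40% of thrombosed venous segments within 3 months after the diagnosis of DVT".
- **Analysis.** The Data Analysis Plan says "All statistical tests will be 2-tailed at a significance level of" 0.05. For continuous measures it lists unpaired t-tests for two groups, one-way ANOVA for three or more, and linear regression for correlation. It gives no paired or repeated-measures method, no missing-data method and no rule for a cleared segment. It asks for subjects with valid measurements but does not say what is valid once the clot has gone.

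**The concern.** The age question draws most of its leverage from day 90, because the other scans all fall within about two weeks of entry. Day 90 is also when the most segments will have lost their thrombus. The clots still measurable then are those that did not completely resolve. If stiffer clots clear less readily, this group is stiffer than the full baseline set for a reason unrelated to age.

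The Background's premise is that thrombus stiffens as it ages, so selection in that direction would look exactly like the expected finding. An unpaired comparison of day 90 with earlier scans cannot tell the two apart.

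Two further gaps add to this. Wall and thrombus readings are not kept apart, so a wall reading from a cleared segment could follow thrombus readings in the same series. And the same segments are scanned repeatedly, while the listed methods treat every reading as independent. What is at stake is the interpretation of secondary objective 6.

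**Working it through.** **Is there a plan figure to reproduce?** No. Target accrual is "30 patients (15 patients with vascular boot vs 15 patients without vascular boot"), and the Data Analysis Plan says "Sample size cannot be calculated statistically due to lack of prior studies in the literature". No effect size, SD or rate is given for elastography.

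**Inputs from the documents (Background).** Share of segments completely clear: at least 5% at 1 week and more than 40% within 3 months. For 6 months the cited figures run from 16% to 75%; I use these as an outer range.

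**Assumed input.** The correlation rho between a clot's stiffness and its tendency not to clear. The documents give no value, so I take 0, 0.3, 0.5 and 0.7.

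**Step 1: thrombus left to measure.** Treat each patient as one unit, which is approximate because the cited rates are mostly per segment. The number left is 30 × (1 − p):
- p = 0.05: 28.5
- p = 0.40: 18, or 9 per arm
- p = 0.16 and p = 0.75: 25.2 and 7.5

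**Step 2: selection shift with no ageing.** Let stiffness and the tendency not to clear be bivariate normal with correlation rho, and let the fraction p most prone to clear drop out. The mean stiffness of the remaining clots exceeds that of all clots, in SD units, by

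shift = rho × φ(z_p) / (1 − p).

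At p = 0.40, z_p = −0.253 and φ = 0.386, so φ/(1 − p) = 0.386/0.60 = 0.644. Multiplying by rho gives the 40% column below; the other columns follow in the same way.

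| rho | 5% cleared | 16% | 40% | 75% |
|---|---|---|---|---|
| 0 | 0 | 0 | 0 | 0 |
| 0.3 | 0.03 | 0.09 | 0.19 | 0.38 |
| 0.5 | 0.05 | 0.15 | 0.32 | 0.64 |
| 0.7 | 0.08 | 0.20 | 0.45 | 0.89 |

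A simulation of 2,000,000 clots at 40% cleared gave 0, 0.192, 0.322 and 0.450. At the 1-week figure the shift is at most 0.08 SD, so the early scans are little affected and the problem sits at day 90.

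**Step 3: the same clots at both times.** Restricting the simulation to clots with thrombus at both scans and taking the difference within each clot gave 0 for every rho. Pairing therefore removes selection on the level of stiffness. It would not remove selection on the rate of change, should clots that stiffen faster also clear less.

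**Step 4: repeat scans.** For one segment measured twice with equal variance σ² and within-segment correlation r, the change has variance 2σ²(1 − r). An unpaired test uses 2σ². Its standard error is therefore wrong unless r = 0, and no listed method estimates r.

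**The case against.** **The bias is hypothetical.** No document figure links stiffness to clearing. At rho = 0 there is no shift, and a negative rho would reverse its sign. The 40% figure comes from another cohort and is per segment. All of this stands, and it is why the size is given as a range from zero. The missing rule for cleared segments and the unpaired treatment of repeat scans do not depend on rho.

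**Conditioning on visible clot is natural for staging, since only a clot that is present needs an age.** This is fair for clinical use. It does not rescue a statement that stiffness rises with age when the old and young groups contain different clots.

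**Much of the remedy is in hand.** Table 2 records clearing by site, and resolution data are collected in both groups. That is true and makes the fix cheap, but the analysis section does not use it.

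A reader might also infer stronger points that the documents do not support:

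- *Nothing is left to measure, or only non-resolving clots contribute.* The vein wall remains a stated target after clearing, and Table 2 includes minimal and partly recanalized clot. The day-90 group is clots not completely resolved.
- *The trial's comparison of stiffness between arms is biased.* No such comparison is named; only the generic two-group t-test could supply one. If 60% cleared with the boot (assumed) against 40% without, the false difference is 0.10, 0.16 or 0.23 SD for rho 0.3, 0.5 or 0.7. With 9 versus 6 patients, the difference detectable at an assumed 80% power is 1.60 SD, and the false-positive rate rises from 5% only to between 5.3% and 6.8%.
- *No clot of uncertain age is studied, so the hope that "these techniques can help decrease the number of age indeterminate thrombus that may result in unnecessary treatment with anticoagulation" cannot be tested.* The entry criteria limit time since diagnosis and exclude "Previous history of DVT or PE". They do not limit time since the clot formed, and the Background says about 30% of DVTs are wrongly staged. That hope is rationale text, not an endpoint.

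**Conclusion.** The concern holds for the stiffness-age analysis at day 90. As listed, the methods would compare day-90 thrombus stiffness in uncleared segments with earlier stiffness in all segments, and would treat repeat scans of one segment as independent. With no ageing at all, the false stiffening at 40% cleared is 0 to 0.45 SD for assumed rho from 0 to 0.7. Over the 16% to 75% outer range, the upper end (rho 0.7) runs from 0.20 to 0.89 SD. The result rests on the bivariate-normal model, the assumed rho and clearing rates borrowed from other cohorts. It concerns a secondary objective of a 30-patient pilot and leaves the primary endpoint untouched. It does not show that any between-arm result is invalid.

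**What to change.** In the Data Analysis Plan:

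1. Analyse thrombus stiffness and wall stiffness as separate variables.
2. State that thrombus stiffness is undefined once a segment is graded No Residual Clot in Table 2, and that no wall value is substituted for it.
3. Estimate change with scan day within segment, among segments with thrombus at both times. Use paired differences, or a mixed model with patient and segment effects. Enter the actual scan day: the windows make day 3 run from day 1 to day 8 and day 10 from day 5 to day 15, so the nominal visits overlap.
4. Report the numbers cleared and the numbers measurable by visit and arm.
5. Treat any day-90 stiffness contrast between arms as descriptive.
6. Describe day-90 stiffness as applying to clots not completely resolved by then.

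Cost: wording and analysis code only, with no new scans or patients. The downside is fewer usable day-90 values (about 18 of 30 if 40% clear) and a more modest elastography conclusion.
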